Fractures in which bone has been exposed through an associated skin injury, known as open fractures, are frequently encountered in orthopaedics. Open fractures traditionally call for formal operative treatment in which the bone is exposed, foreign tissue is debrided and the wound is irrigated. Open fractures can differ in terms of the bone involved, energy causing the injury and the skeletal maturity of the patient. Children, for example, have a thick periosteum which may decrease healing time and diminish the infection rate due to its robust blood supply. In addition, operative debridement was introduced at the same time as widespread antibiotic use. It is not known whether the mechanical operative management or antibiotic use has resulted in improved outcomes. In retrospective studies, centers are reporting that non-operative treatment may result in comparable outcomes without the time and expense of the operative theater.

The potential advantages of non-operative treatment include shorter hospital stays, avoiding the risk of general anesthesia, lower costs and lack of a larger incision. Still, operative debridement has minimal additional morbidity, so for a child to be treated nonoperatively, the infection rate must not be significantly different from the gold standard operative management. In order to compare these two different treatments, a prospective randomized non-inferiority trial is necessary and warranted. Either patients are going to the operating room when emergency room treatment will be adequate or they are receiving inadequate care when they avoid operating room management.

C. Historical Review:

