Of the thirteen patients who agreed to participate, six were randomized to emergency room treatment and seven were randomized to operating room treatment. One of the patients, randomized to operating room treatment fracture was NOT found to have an open fracture and

will be eliminated from final formal assessment beyond intent to treat analysis. Another patient who was randomized to the operating room chose not to undergo surgery and instead received ED treatment only. None of the twelve patients' fractures, enrolled in the study, were complicated by infection or delayed healing. There have been no differences in anesthesia/sedation related complications.

E. Methods:

Clinical Trial Portion

Design of the study: A prospective, randomized unblinded non-inferiority clinical trial of children with Type I open fractures to evaluate whether emergency room management and close follow up will not be inferior to formal operative irrigation and debridement in terms of infection rates and bone healing times. The baseline rate of infection with open fractures, treated operatively, is noted to be 0-10% in the literature. We will choose a baseline infection rate of 1%.

Study population:

Inclusion Criteria - Patients will be included if their age is between 3 and 14 years, if the fracture is amenable to treatment by closed reduction, a low energy injury (falls from less than 10 feet, bicycle accidents), wounds less than 1 cm in length and the bone not visualized through the skin.

Exclusion Criteria - Patients will be excluded if they do not meet inclusion criteria, if the fracture would typically require operative reduction and fixation, if their mechanism was high energy (struck by vehicle, motor vehicle accidents, fall from height greater than 10 feet), if there is gross contamination of the wound, or if the open injury involved the hands or feet (the current standard of care to treat open injuries involving hands or feet is only emergency room management).

Study Procedures:

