(Specific Aim 2) Union of the fracture will be determined by radiographic parameters of callous being on three of four sides of bone without tenderness to palpation. The radiographs will be read by the attending orthopaedic surgeon at each clinic visit to determine treatment. Loss of reduction will be noted but will not be considered a complication since it can occur whether or not operative debridement was performed. A revision reduction can be performed at the attending orthopaedic surgeon's discretion. In the final analysis phase, an orthopaedic surgeon, blinded to the treatment, at Lurie Children's will be utilized to review all of the patient's radiographs to determine bridging callous on three sides of the bone. This reviewer will be blinded to the patient's name, treatment group but will have access to the length of time since the fracture occurred. Additional procedures or deviations from the protocol will be noted. We will

also carefully examine the rates of anesthesia and sedation related complications including nausea and vomiting, respiratory depression, aspiration, hoarseness, and emergence agitation.

Sample size assumptions and estimates:

This will be a non-inferiority trial as we attempt to demonstrate that ED management is not inferior to OR management.

For the binary outcome of infection (**Specific Aim 1**), we estimate an infection rate of 1% in the reference (OR) group since the literature notes an infection rate between 0% and 5%. Based on a survey of pediatric orthopedic surgeons, an acceptable margin of non-inferiority can be estimated at approximately 4% (i.e., accept a 5% infection rate in the ED group), as the survey suggests surgeons will accept a 5% infection rate in order to avoid formal operative treatment of children with open fractures. We will test the following hypotheses: $H_0: P_T - P_C \geq \Delta$ vs. $H_1: P_T - P_C < \Delta$. In order to test these hypotheses in a non-inferiority design at the one-sided 2.5% level of significance, we will construct a two-sided 95% confidence interval for the difference in proportion of infections ($P_T - P_C$) across the two groups. If the upper confidence limit is less than our acceptable margin of non-inferiority ($\Delta=4\%$), then we would conclude ED management is not inferior to OR management with respect to infection rates.

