Our results suggest that a **sample size of 150 per group (300 total)** would provide 91% power to detect non-inferiority of emergency room management when compared to operating room treatment in the type one open fractures under the assumptions outlined above. We have accepted a 5% infection rate (4% shift from the hypothesized reference rate). If the baseline infection rate is 2%, this study would be adequately powered (87%) to show non-inferiority for a margin of 5% (7% infection rate in the ED arm). As the calculation above illustrates, the study is also well powered to demonstrate non-inferiority with respect to healing time.

Site estimates:

The following sites have provided the initial estimates as to how many patients they feel could be enrolled in a given year: Lurie Children’s = 2/year, Vancouver Children’s Hospital 5/y, Riley Children’s= 2/y, University of Mississippi Medical Center = 9/y, Mary Bridge Children’s Hospital= 12/y, Yale-New Haven Children’s Hospital= 4/y, Carrie Tingley Children’s Hospital= 20/y, Phoenix Children’s Hospital= 20/y, Nationwide Children’s Hospital= 20y, IWK Health Centre, Halifax=4/y, Denver Children’s Hospital=12/y. Texas Children’s Hospital= 12/y, Morristown Medical Center = 2/y, New York University Medical Center = 4/y. Approximate Total= 128/y.

Subject Recruitment:

The number of subjects needed for this trial is large. To date, the pilot study has had an excellent recruitment (80% see below) rate, so we expect similar rates at participating centers.

Currently, with the 14 sites who have agreed to participate thus far, the expected recruitment is 128 patients per year. We plan to add 4-6 more sites during the Planning Grant Period which would expand the projected total recruitment to 160 patients per year. Therefore, when the study is at full capacity, we conservatively anticipate recruiting 120 patients per year (assuming 75% recruitment rate) over the 3 year grant period, for a total of 360 patients, which surpasses the calculated 300 patients needed for adequate statistical power. We are accepting and powering for a 5% infection rate in the ED arm. If we were to accept a 6% infection rate (i.e., a 5% margin of non-inferiority) then we would require only 190 patients. For a 7% infection rate ($\Delta=0.06$), we will need 150 patients. If recruitment is lower than expected, we could accept a larger

margin of non-inferiority given the large range of type I open fracture rate (0-10%) in the literature.

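### The 4-point infection margin rests on a clinical judgement, but the plan allows it to be widened if recruitment is low, for a reason that does not support a larger excess

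*Combined protocol and SAP*

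**What the plan says.** In the combined protocol and SAP, E. Methods, Sample size assumptions and estimates takes 1% as the OR infection rate and puts the acceptable excess at about 4 points, "as the survey suggests surgeons will accept a 5% infection rate in order to avoid formal operative treatment of children with open fractures". The rule is one-sided at 2.5%: "If the upper confidence limit is less than our acceptable margin of non-inferiority", with Δ = 4%, ED management is declared not inferior.

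Subject Recruitment then gives smaller trials for wider margins: "If we were to accept a 6% infection rate (i.e., a 5% margin of non-inferiority) then we would require only 190 patients", and for a 7% ED rate (Δ = 0.06) "we will need 150 patients". It continues: "If recruitment is lower than expected, we could accept a larger" one. The ground it offers is the spread of published rates: "margin of non-inferiority given the large range of type I open fracture rate (0-10%) in the literature".

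Three other places bear on this:
- Design of the study says what the range refers to: "The baseline rate of infection with open fractures, treated operatively, is noted to be 0-10% in the literature".
- The paragraph that states the planned 150 per group adds that, with a 2% baseline, the trial has 87% power for a 5-point margin.
- The analysis section (the Data Analysis heading after Data management) refers to the margin without giving its value, and says that normal-approximation and exact intervals will both be explored.

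**The concern.** A non-inferiority margin states how much worse the new treatment may be and still be acceptable. Here that is a clinical judgement with a stated source, the surgeon survey. Slow recruitment does not alter what surgeons or families would tolerate. The literature range describes infection after operative treatment, so it conveys uncertainty about the OR rate and not tolerance of a larger excess over it. The Significance section leans the other way: operative debridement adds little morbidity, "so for a child to be treated nonoperatively, the infection rate must not be significantly different from the gold standard operative management".

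The plan also does not say who would change the margin, by when, or without sight of which data. The trial is unblinded, and under Interim monitoring every infection is discussed by the principal investigator and site leaders. Subject Recruitment further allows a halt and release of results at 150 patients if the two arms' rates are nearly equal. That is the same total the plan pairs with 6 points.

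At stake is a headline claim of non-inferiority for children's care that would not meet the only margin the protocol justifies.

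**Working it through.** **Inputs.** From the sample size section: OR rate 1%, margin 4 points, upper limit of a two-sided 95% interval. From Subject Recruitment: 190 patients for 5 points and 150 for 6. With 1:1 allocation these are 95 and 75 per arm. They are read as totals because they are set against the planned total of 300. No dropout is applied.

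**Formulas.** With d = pT − pC (observed, ED minus OR):
- Wald upper limit: d + 1.96·√[pT(1−pT)/n + pC(1−pC)/n].
- Newcombe upper limit: d + √[(uT−pT)² + (pC−lC)²], where u and l are Wilson limits.
- Chance of a claim: the sum, over all pairs of infection counts whose upper limit is below the margin, of Bin(xT; n, πT)·Bin(xC; n, πC), where πT and πC are the true rates.

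**Reproducing the plan.** With 1% in both arms, 150 per arm and 4 points, Wald gives 91.05% (plan 0.9111) and Newcombe 69.4%. With 2% in both arms and 5 points, Wald gives 87.7% (plan 0.8785). The power table therefore follows the Wald rule. Wald power is 93.4% at 95 per arm with 5 points and 89.8% at 75 per arm with 6 points, which supports reading 190 and 150 as totals.

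**Effect of widening.** Take true rates of ED 5% and OR 1%. The difference is exactly 4 points, which lies in the plan's null hypothesis. The chance of claiming non-inferiority is:

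| Per arm | Margin | Newcombe | Wald |
|---|---|---|---|
| 150 (planned) | 4 | 1.9% | 5.2% |
| 95 | 4 | 1.9% | 5.3% |
| 95 | 5 | 3.8% | 15.2% |
| 75 | 4 | 1.5% | 10.7% |
| 75 | 6 | 7.3% | 19.4% |

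**Newcombe at 75 per arm, by hand.** For ED, P(0) = 0.95^75 = 0.0213, P(≤1) = 0.1056 and P(≤2) = 0.2697. For OR, P(0) to P(4) are 0.4706, 0.3565, 0.1332, 0.0327 and 0.0060.
- 4 points: a claim needs 0 ED infections when OR has 1 or 2, and at most 1 when OR has 3 or 4. This gives 0.4897 × 0.0213 + 0.0387 × 0.1056 = 0.0104 + 0.0041. OR counts of 5 or more add 0.0003. Total 0.0148.
- 6 points: a claim needs 0 ED infections when OR has 0, at most 1 when OR has 1 or 2, and at most 2 when OR has 3 or 4. This gives 0.4706 × 0.0213 + 0.4897 × 0.1056 + 0.0387 × 0.2697 = 0.0100 + 0.0517 + 0.0104. OR counts of 5 or more add 0.0005. Total 0.0727.

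**Two example results at 75 per arm.**
- 1 against 1 infection: the Newcombe upper limit is 5.9%, which fails 4 and passes 6. The Wald limit is 1.96·√(2 × 0.01333 × 0.98667/75) = 3.7%, which passes 4.
- 2 against 2: the Wald limit is 5.2%, which fails 4 and passes 6. The Newcombe limit is 6.8%, which fails both.

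**The wider tests at their own boundaries.** With OR 1% and ED 6% (5 points, 95 per arm) Newcombe gives 1.7%. With ED 7% (6 points, 75 per arm) it gives 2.0%. The corresponding Wald figures are 7.8% and 6.6%.

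**The case against.** A reader might infer that a movable margin destroys the one-sided 2.5% error rate. For this rule it does not. At a fixed sample size the coverage of a 95% limit does not depend on the margin it is compared with, and at true rates of 5% and 1% the statement that the excess is below 6 points is correct. The Newcombe results at the wider boundaries, 1.7% and 2.0%, bear this out. The table above therefore shows the chance of a claim that is wrong by the 4-point standard. It does not show the type I error of the wider test.

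Part of the Wald increase belongs to the interval: Wald already gives 10.7% at 75 per arm with 4 points. The plan names no interval and leaves exact methods open. Subtracted Clopper-Pearson limits give only 0.8% (95 per arm, 5 points) and 2.2% (75 per arm, 6 points). Both qualifications stand.

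The sentence is also conditional, its stated trigger is recruitment and not outcome, and the alternatives with their sizes are disclosed beforehand. A reader should not infer that the sponsor has committed to widening or intends to choose the margin from the results; the documents say neither. Each site sees only its own records in the database (Data Security), although infections are discussed across sites.

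The Significance wording is background and, read literally, would count against 4 points too. Interim monitoring also uses 0-10% for presumed infection rates in the trial generally. Even on that reading, a spread of rates does not say how much excess is tolerable.

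**Conclusion.** The concern holds as a defect in the justification and control of the margin. The plan gives a clinical reason for 4 points and none for 5 or 6, yet leaves the larger margins available when the trial is short. With Newcombe, which separates the margin effect from the interval's own error better than Wald, applying the wider margin roughly doubles the chance of a claim at 5% against 1% with 95 per arm, and raises it about fivefold with 75 per arm.

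These sizes assume that the wider margin is actually applied, equal arms, no dropout and a 1% OR rate. At 6% against 2% the wider-margin figures are similar: Newcombe 3.9% and Wald 10.7% at 95 per arm with 5 points; 6.9% and 15.3% at 75 per arm with 6 points. Whether the result exceeds 2.5% depends on the interval. The lack of support for the wider margin does not.

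**What to change.** 1. In Subject Recruitment, delete the sentence that lets the margin grow when recruitment is low.
2. In the Data Analysis section that gives the decision rule, state that the infection margin is 4% whatever the recruitment or the observed baseline rate.
3. Label the 190- and 150-patient figures as sensitivity information only. Do the same for the statement of 87% power at a 5-point margin with a 2% baseline; otherwise it remains a second route to a wider margin.
4. If recruitment falls short, including a halt at 150 patients, report the 95% interval against 4% and call the result inconclusive if the interval crosses it.

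This changes wording only. The price is that a short trial may not reach a conclusion. Power at 4 points with 1% in both arms is 77% (Wald) or 48% (Newcombe) at 95 per arm, and 83% or 26% at 75 per arm. The higher Wald figure at the smaller size reflects the discreteness of small counts and that interval's excess error; it is not a gain from fewer patients.

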Baseline assessment will include the child's age, mechanism of injury, bone fractured, wound side and location, state of skin injury, whether gross contamination is present, neurovascular status, comorbid conditions.

Additionally, if patients do not wish to be randomized to a treatment arm, they will still be presented with an option for study enrollment. They may take part in a prospective chart review in which the same data will be collected as those patients who were randomized. The data collected at both the baseline and follow-up will match the data collected from patients who randomized to a treatment arm. Patients will consult with their physician regarding treatment for their injury and decide which treatment method they prefer. They will then be consented by the study coordinator or an investigator who will describe the study and the data that will be gathered from their medical charts.

Intervention allocation:

The randomization assignment will be completed and accessible only by the study coordinator. The coordinator will have the assignments in numbered, sealed, radio opaque envelopes in sequential order by the study site. The envelopes will be made by an independent study assistant and determined by block allocation with a 1:1 ratio of operative room vs. emergency room management with permuted, mixed blocks of 4 and 6 created randomly. Randomization will be stratified by each center but by no other factors. The order of these permuted blocks will be determined by random number chart.

Experimental and Control Interventions:

Children will be randomized into two treatment arms – formal operative management (OR) and emergency department (ED) management. Children randomized to the OR arm will be taken to the OR within 24 hours for irrigation and debridement and appropriate bone management. Patients who randomize to non-operative treatment will only be given conscious sedation in the emergency department where the bone will be reduced and casted and the wound will be washed out with one liter of normal saline. All patients will be admitted for 24 hours of intravenous antibiotics post treatment and then sent home with 7 days of oral antibiotics.

Follow up visit description and schedule:

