If we are only able to recruit 150 patients, and the rates of infection in the OR and ED groups are nearly equal, we will consider halting the study and releasing the results. This will be decided by the Steering Committee in conjunction with the funding agency. Alternatively, the Steering Committee could decide to prolong the study to achieve increased numbers for the comparison.

Data management:

An initial hard copy survey of the initial data will be completed by the attending surgeon with the study coordinator's assistance. Data collected will include name, MRN, telephone number, age, injury mechanism, bone fractured, wound size (in cm), wound location, state of skin, neurovascular status, comorbid conditions, antibiotics given, tetanus status, surgical procedure description and anesthesia/sedation complications. At the 1-week follow up visit, a survey will be completed by the attending surgeon which will ask if fevers are/have been present, wound drainage through cast, skin and wound examination (erythema, drainage), whether additional antibiotics are necessary, and the reduction of the bone on radiographs. The survey completed by the treating orthopaedic surgeon at subsequent visits will also ask if fevers are presents, if pain has increased, wound drainage, if a second look at the wound was necessary, reduction of the fracture, and healing.

An online database has been created using REDCap technology. Name, MRN and telephone number will be recorded in site-specific Excel files. Non-identifying data will be recorded in REDCap. Information from the initial and follow up visits will be entered into the databases by the surgeon or his representative which will be password protected. Each patient will have a unique identifier. Randomization allocation can also be found through the REDCap site.

Data Analysis:

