personnel. The five sites will be utilized to insure that the recruitment operation, site randomization, and organizational procedures are in place. All data will be run through, housed and analyzed at Lurie Children's. Finally, eight to ten additional sites, (locations to be determined) will be recruited, for a total of 13 -15 sites, each with their own Site Leader to complete the recruitment and treatment of patients.

Study Administration:

Executive committee: This will be made up of the Primary Investigator, Site Leaders from the 5 sites indicated above, and one volunteer from an external site not directly enrolling in the study. They will be in charge reviewing protocol deviations, counseling on study issues, and noting complications. They will meet monthly.

Steering committee – This will be made up of the Primary Investigator and all Site Leaders. They will be in charge of overall organization and will determine if an unsatisfactory rate of infection (>10%) is found.

Funding organization – Funding for the study will be attempted after phase 2 has been completed through NIH and the Pediatric Orthopaedic Society of North America. Funding will be needed for study coordinators and administrative needs. Phase 3 funding will be attempted through NIH and the Orthopaedic Research Education Fund.

Ethical issues:

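### If accrual stops at 150 patients, the decision to halt or prolong turns on an undefined near-equality of the OR and ED infection rates, which is not the trial's non-inferiority criterion

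*Combined protocol and SAP*

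**What the plan says.** The last paragraph of Subject Recruitment covers a shortfall: "If we are only able to recruit 150 patients, and the rates of infection in the OR and ED groups are nearly equal", halting and releasing the results will be considered. The Steering Committee decides together with the funding agency. The next option is open-ended: "Alternatively, the Steering Committee could decide to prolong the study to achieve increased numbers for the comparison". Study Administration describes that committee: "This will be made up of the Primary Investigator and all Site Leaders".

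The success criterion is elsewhere. Sample size assumptions and estimates tests non-inferiority "at the one-sided 2.5% level of significance" and concludes it "If the upper confidence limit is less than our acceptable margin of non-inferiority", with the margin set at 4 percentage points. The Data Analysis section that follows Data management repeats the confidence-limit rule. It does not fix the interval: normal-approximation and exact methods are both to be explored.

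The paragraph just before the halting text pairs 150 patients with a 6-point margin and says a larger margin could be accepted if recruitment falls short. The planned size for 4 points is 300.

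**The concern.** Closing a trial because accrual has failed is legitimate. Here a second condition is added: the observed comparison between arms on the primary outcome. The people judging it are the investigators who enrol and treat, together with the funder, in an unblinded trial. Near-equality has no definition, boundary or error adjustment, and no confidence limit is attached to it. An unspecified, result-dependent choice of this kind cannot be corrected for in the analysis.

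Similar point estimates are also not what the trial set out to show. Near-equality at 75 per arm does not by itself establish that the excess is below 4 points. With the neighbouring sentence on a wider margin, a reader could take similar rates at 150 patients as sufficient. At stake is whether a truncated Aim 1 result is credible and how it may be described.

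**Working it through.** **Inputs.** One-sided 2.5% level. OR rate: "we estimate an infection rate of 1% in the reference (OR) group". Margin: "an acceptable margin of non-inferiority can be estimated at approximately 4" percentage points. Allocation: "block allocation with a 1:1 ratio of operative room vs. emergency room management" (Intervention allocation), so 150 patients means 75 per arm. The 150 is read as a total, because the same section compares accrual with 300 patients needed.

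**Step 1: reproduce the protocol's table.** Power is the exact binomial probability that the Wald upper limit, d + 1.96 × √[pT(1−pT)/n + pC(1−pC)/n], lies below 0.04, where d = pT − pC and the proportions are those observed. With equal true rates:

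| Per arm | True rate | Recomputed | Protocol table |
|---|---|---|---|
| 70 | 1% | 0.6723 | 0.6766 |
| 80 | 1% | 0.8104 | 0.8107 |
| 150 | 1% | 0.9105 | 0.9111 |
| 150 | 2% | 0.7061 | 0.7048 |

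The table therefore rests on the uncorrected Wald interval.

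**Step 2: power at 75 per arm, 4-point margin.** Wald gives 82.8% at 1% and 57.3% at 2%. Newcombe (built from Wilson limits) gives 26.3% and 24.0%.

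**Step 3: what equal counts show at 75 per arm.**

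- Wald, 1 v 1: p = 1/75 = 0.01333, and 1.96 × √(2 × 0.01333 × 0.98667/75) = 0.0367, which is below 0.04.
- Wald, 2 v 2: p = 2/75 = 0.02667, and 1.96 × √(2 × 0.02667 × 0.97333/75) = 0.0516, which is above 0.04.
- Newcombe, 0 v 0: the Wilson upper limit is 3.84/(75 + 3.84) = 0.0487, and this is also the limit for the difference.

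| ED v OR infections | Wald upper limit (points) | Newcombe upper limit (points) |
|---|---|---|
| 0 v 0 | 0.0 (zero width) | 4.87 |
| 1 v 1 | 3.67 | 5.94 |
| 2 v 2 | 5.16 | 6.82 |
| 3 v 3 | 6.27 | 7.58 |

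Equal counts of 0 or 1 meet 4 points with Wald. No equal count does with Newcombe.

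**Step 4: effect of the halt if it is exercised.** Model: look at 75 per arm, halt if the counts are equal (or differ by at most 1), otherwise continue to 150 per arm. A claim requires the upper limit to be below 4 points at whichever size is final. All outcomes are enumerated.

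| Design | Wald: false claim (ED 5%, OR 1%) | Wald: claim (1%, 1%) | Newcombe: false claim | Newcombe: claim (1%, 1%) |
|---|---|---|---|---|
| Fixed 150 per arm | 5.2% | 91.0% | 1.9% | 69.4% |
| Halt if equal | 7.6% | 90.5% | 1.25% | 40.6% |
| Halt if within 1 | 11.1% | 87.8% | 1.15% | 27.0% |
| Fixed 75 per arm | 10.7% | 82.8% | 1.5% | 26.3% |

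**The case against.** Several stronger readings are tempting, and the documents do not support them.

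- A reader might infer that equal rates at 150 patients cannot meet the margin. On the interval behind the protocol's own table, 0 v 0 and 1 v 1 both meet it. Given equal counts at a true 1%, the chance of meeting it is 94.9%. The inference is right for Newcombe, which the documents never name. With Wald it is right once each arm has 2 or more infections.
- A reader might infer that the halt both inflates false claims and destroys power. No single interval does both to any marked degree. With Wald the power loss is small, and with Newcombe the false-claim rate falls.
- A reader might blame the whole rise to 11.1% on the stopping rule. A fixed trial of 75 per arm with no such rule already has 10.7% under Wald, so much of the rise is small-sample error of that interval.
- A reader might see a scheduled look with a binding stop. The text is a contingency for an accrual shortfall and says only that halting will be considered. Prolonging is an alternative with no stated trigger. If accrual has stalled, 150 per arm may be out of reach as a comparator.
- Releasing results is not itself a claim of non-inferiority. The confidence-limit rule still governs that claim.

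These points limit the size of the problem and make it depend on the interval. They do not remove it. The condition still refers to the primary comparison, is still undefined, and is left to the investigators' committee with the funder. Discretion makes the effect harder to quantify or adjust for.

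**Conclusion.** The point holds in this form: in the event of a shortfall at 150 patients, the plan permits an undefined, unadjusted, result-dependent halt, and near-equality is not evidence of meeting the 4-point margin. It should be fixed. It does not show that a trial halted at 150 must fail or must mislead.

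By the protocol's own method, power at that size is about 83% at 1% and 57% at 2%, against 91% and 71% at the planned size. If the halt is used, the cost is either more false claims (Wald: 5.2% to 7.6% or 11.1%) or a smaller chance of a conclusive trial (Newcombe: 69% to 41% or 27%).

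The power figures assume a 75/75 split and no dropout, for which the documents give no allowance. The halt figures also assume that near-equal means counts equal or within one infection, that the halt is always taken when that is met, and that the trial otherwise reaches 300.

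**What to change.** All edits are in Subject Recruitment.

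1. Delete the near-equality condition. Base the choice between halting and prolonging on accrual and funding only, without using the between-arm infection comparison.
2. State that a trial ending below 300 patients is judged by the unchanged rule (upper 95% limit below 4 points) and is reported as inconclusive if that is not met.
3. Remove the sentence allowing a larger margin when recruitment is low. Otherwise it contradicts item 2.

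Leave the safety rule in Termination policy as it is. The trial is unblinded and site leaders discuss every infection, so the committee will still know arm-level events. The edit restricts what may drive this decision, not what the committee may see.

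The cost is a few sentences, and the sponsor loses the option to stop because the comparison looks favourable. The edit removes the result-dependence of stopping. It does not restore power at 150 patients: a halt there on accrual alone still has a 10.7% false-claim rate with Wald, or a 26% chance of a claim at 1% in both arms with Newcombe. The Wald interval's small-sample error is a separate issue.
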